9.3.1 Unscheduled Visit

An unscheduled visit can be held at any time during the study, if deemed necessary by the investigator. In addition, an unscheduled visit must be scheduled to occur as soon as possible if an AESI is reported during any telephone contact. An unscheduled visit will not replace any of the above visits as per schedule of events. Assessments performed at an unscheduled visit will be at the investigator's discretion, but should include AE assessment, AESI query, concomitant medication and possibly FWS.

In case of an unscheduled visit, the investigator should complete the “Unscheduled Visit Form” in the CRF.

9.4 Subject Diary and Patient Reported Outcomes

9.4.1 Subject Diary

A paper subject diary will be provided to each subject at the baseline visit (day 0) and one week after the first treatment visit to record the following information:

- Daily documentation of FWS score at maximum frown.

The subject diary will be collected at the visit one week after the first treatment and the subject will be given a second diary to be returned at the visit two weeks after the first treatment. Subjects will be trained on use of the diary during the baseline visit (training will be recorded in the source and the CRF).

Treatment onset will be evaluated by the subject and the investigator (using FWS) at study visits one, two and four weeks after the first treatment and documented accordingly. In addition, for further determining onset of treatment, the subject will record the FWS score in diaries daily for the first two weeks after treatment (in the first treatment cycle).

The subject diary will serve as a source record and remain at the study site. Entries in the subject diary will be transcribed into the electronic data capture (EDC) system by the blinded member of the site study team.

9.4.2 Patient Reported Outcomes

A patient-reported outcome (PRO) instrument (i.e. a questionnaire plus the information and documentation that support its use) is a means to capture patient, or subject views of outcomes used to measure treatment benefit or risk in IMP clinical trials. Three PRO instruments will be used in this study to support claims in the product label, comprising:

- The FWS, which will be used to evaluate the severity of glabellar lines (Section 20.1 and Section 10.1) which will be completed by the subject (PRO) and the investigator (clinician reported outcome).
- The modified Skindex-16 (GL-QoL) and FACE-Q scales (Appraisal of Lines Between Eyebrows and Age Appraisal VAS scales), which will be used to measure the psychological impact of glabellar lines and concerns relating to their glabellar lines, respectively (Section 20.3 and Section 20.4, Section 20.5).

- The FACE-Q Satisfaction with Outcome Scale which will be used to measure subject satisfaction with treatment (Section 20.6).

Entries in the questionnaires will be transcribed into the EDC system by a blinded member of the site study team.

9.5 Subject Completion/Discontinuation

A subject is considered to have completed the study when he/she ceases active participation in the study because the subject has, or is presumed to have, followed all appropriate conditions of a protocol (with or without protocol deviations). Completion of the first cycle and the open label cycles will be documented on two different CRF pages.

Subjects will be considered to be "per protocol completers" of Cycle 1 if they had no significant protocol deviations **in the first cycle** and an in-clinic assessment with the FWS by the investigator and the subject at baseline (day 0) and at the week 4 visit were performed.

Subjects will be considered to be "per protocol completers" of the study if they have completed the final cycle within week 48-60, without significant protocol deviation.

Reasons for completion or non-completion will be reported on the Completion/Termination CRF, including: completed, screen failure, premature termination due to AE (including death), discontinuation by subject (e.g. dropout, lost to follow-up, withdrawn informed consent), physician decision (e.g. non-compliance with protocol, or for safety reasons), study terminated by Sponsor, or other reason to be specified by the investigator. Regardless of the reason for subject withdrawal, all data available for the subject up to the time of completion/discontinuation should be transferred from the subject records on the appropriate CRF.

Every effort will be made to have discontinued subjects complete the End of Study visit. All procedure and assessment results performed at such visits will be recorded under the Termination visit assessments. If a subject terminates participation in the study during or after a visit and does not return for a Completion/Termination visit, their last recorded assessments shall remain under the last visit they attended (i.e. no assessment data shall be recorded under/transferred to the Completion/Termination visit assessments). The reason for discontinuation will be recorded on the CRF.

9.6 Procedures for Monitoring Subject Compliance

All study procedures are to be performed under supervision at the study site, and thus, no separate procedures will be used to monitor subject compliance.

10. ASSESSMENT OF EFFICACY

10.1 Assessment of Glabellar Line Severity: Facial Wrinkle Scale

In accordance with FDA Guidelines for Upper Facial Lines, efficacy will be determined using well defined, valid and reliable clinician-reported and subject-reported assessments, capable of measuring the critical outcomes that contribute to a conclusion of overall success or failure. For both investigator and subject assessment, measurements will be made at maximum frown (which represents the worst appearance of upper facial lines with maximum load on the muscle) and at rest (which represents the best appearance of upper facial lines with the least load on the muscle), which allows one to impute benefit when the face is in dynamic motion (variable load on the muscle).

The scale used most frequently in clinical studies is the FWS, which is a four-point rating scale as follows: 0 = no facial wrinkles; 1 = mild facial wrinkles; 2 = moderate facial wrinkles; and 3 = severe facial wrinkles. The scale has been validated and shown to be reproducible⁴². However, this scale includes pictures at rest and at maximum frown within the one scale, meaning that the sensitivity of the scale at rest is low. The instrument proposed for use in this study is the FWS (Glabellar Line Scale for Investigators [GLS-I] and Glabellar Line Scale for Subjects [GLS-S]), as described in Section 20.1. The FWS instrument is termed GLS-S and GLS-I. The scale and the proposed instructions for its use by investigators and subjects are described in Section 20.1 and in the Instruction Manual for Subject Glabellar Line Severity Self-Assessment.

10.1.1 Subject and Investigator In-clinic Assessment

Subjects will be trained extensively in accurate self-assessment of their glabellar line severity by the investigator at the baseline visit, as outlined in the Instruction Manual for Subject Glabellar Line Severity Self-Assessment. Investigators will complete training before trial initiation and will receive training certification. Subject assessment must be performed independently of the investigator and ideally before the investigator assessment, to rule out any influence or bias from the investigator. The date and time of assessment will be recorded for each visit in the double blind cycle and for the week 4 visits during the open label cycles. Subjects and investigators will assess the severity of the subject's glabellar lines at maximum frown and at rest using the FWS instrument (Section 20.1), i.e. the GLS-S (for subjects) and the GLS-I (for investigators).

In the first treatment cycle, the severity of the subjects' glabellar lines will be evaluated by the subject and the investigator at baseline and at study visits 1, 2, 4, 8, 12 weeks and at 4 weekly intervals thereafter (week 16, week 20, etc.) until the subject qualifies for re-treatment with glabellar line severity returning to a score of 2 or 3 on the FWS. The same investigator must assess the subjects at baseline and at the visits at weeks 1, 2 and 4 in the first treatment cycle, although every effort shall be made to have the same investigator assess subjects at all time points.

The primary efficacy endpoint will be a composite endpoint of the investigators' and the subjects' assessments of line severity at maximum frown in comparison with placebo at week 4. A subject will be considered a responder if they have a FWS score of 0 or 1 and an improvement ≥ 2 points in FWS score (at maximum frown) at the week 4 visit (of the first treatment cycle) relative to baseline, based on both the investigator's and the subject's in-clinic assessments. Responder rates at other time points in the first treatment cycle will be evaluated as secondary endpoints.

In the open label extension phase, the percentage of responders (FWS score of 0 or 1 and an improvement ≥ 2 points in FWS score at maximum frown) at week 4 after re-treatment relative to the rating at the preceding end of cycle visit will be determined as a secondary efficacy endpoint.

10.1.2 Photo-evaluator Assessment

Photography will be performed by specifically trained personnel in accordance with the relevant imaging manual. Photographs of subjects at maximum frown and at rest will be taken in the first treatment cycle at the following visits: baseline before the first treatment, study visits 2 and 4 weeks after the first treatment and at the Evaluation for Re-treatment visits, i.e. week 12 after baseline and 4 weekly thereafter until the subject qualifies for re-treatment. Selected photographs will subsequently be assessed by independent blinded raters, however, although a photograph will be taken at each evaluation for the re-treatment visit, only the photograph of the visit preceding the re-treatment visit will be reviewed by the independent raters (in addition to the photographs at baseline, week 2 and week 4) and the data will be included in the analysis of additional secondary efficacy endpoints.

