4.5.1.2 Justification for Schedule

The study schedule includes a maximum of four permitted treatments per subject (four treatment cycles), separated by a minimum interval of 12 weeks, during the study time frame of up to 60 weeks in treatment phase. A minimum interval of 12 weeks between treatments was selected, since the median duration of effect has been reported to be 85 days (12.1 weeks)³¹ and this treatment interval has been evaluated in several repeat treatment studies^{32,33}.

However, since treatment duration of 120 days³⁴, 17.1 ± 6.5 weeks³⁵ or four to six months³⁶ have been reported and re-treatment intervals have been estimated at a mean of 3.9 months³⁶, the schedule has been devised flexibly such that subjects can obtain re-treatment when they qualify (according to the "Eligibility Criteria for Re-

treatment" Section 7.3), which can be at week 12 at the earliest or at four weekly intervals thereafter. Hence, the duration of effect of BoNT/-DP will be evaluated in the first treatment cycle compared with placebo. The duration of effect of BoNT/-DP after repeat treatment will be assessed in the open label extension study. The duration of effect has been reported to increase with repeat treatment³⁷.

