7.3 Eligibility Criteria for Re-treatment

The following criteria **MUST** be met for re-treatment:

- At time of re-treatment subject does not have relevant changes to their health status from enrollment, which would have prevented subject's entry into the study according to the inclusion and exclusion criteria.
- The subject must have been randomized to receive treatment and must have received at least one treatment (BoNT/A-DP or placebo).
- A minimum of 12 weeks must have elapsed since the previous study treatment.
- The subject's glabellar lines at maximum frown must have relapsed to a FWS score of 2 or 3 as determined by both the investigator and the subject.
- No relevant infection or inflammation in the planned injection area.
- Negative urine pregnancy test, in women of child-bearing potential.
- The subject must have received fewer than four study treatments.
- The subject must agree and consent to re-treatment.
- Re-treatment will be performed at the latest by week 48.

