- 10 Photographs of subject's glabellar lines (at maximum frown and at rest) will be taken at C1 Randomization, C1 week 2, C1 week 4 and each C1 Evaluation for Re-Treatment visit in Cycle 1 until the subject qualifies for re-treatment in order to provide evidence of effect and confirm that the subject did not qualify for re-treatment on the preceding evaluation for re-treatment visit. Although a photograph will be taken at each Evaluation for Re-treatment visit, only the photo of the visit preceding the re-treatment visit will be reviewed by the independent reviewers.
- 11 Modified Skindex-16 (GL-QoL) and FACE-Q Appraisal of Lines Between Eyebrows and Age Appraisal VAS scales will be used to measure psychological impact and concerns relating to their glabellar lines, respectively (and will be recorded in the CRF).
- 12 Treatment satisfaction will be determined using the FACE-Q Satisfaction with Outcome Scale (will be recorded in the CRF).
- 13 Subjects will be monitored for AEs during 30 minutes after administration of the IMP. No additional questioning of AESIs directly post-injection.
- 14 Anti-drug-antibody (ADA) test. If positive, serum samples will be tested for the presence of neutralizing antibodies.
- 15 AESI Questioning: active questioning by guided review of systems (ROS) as per AESI manual. If an AESI is reported, a targeted physical examination around the area of the reported AESI must follow.

AE: Adverse event; AESI: Adverse event of special interest; C: Cycle; CRF :Case report form; D:Distribution of subject diary; ECG: Electrocardiogram; FWS: Facial Wrinkle Scale; GL-QoL: Glabellar Line Quality of Life Scale; IMP: Investigational medicinal product; R:Return of subject diary; TC: telephone call; VAS: Visual analog scale

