4.3 Additional Secondary endpoints

The additional secondary endpoints of this study are:

6. The proportion of responders among BoNT/A-DP and placebo groups with a FWS score of 0 or 1 and an improvement ≥ 2 points in FWS score (at maximum frown) during the first treatment cycle visit relative to baseline, based on both the investigator's and the subject's in-clinic assessments (composite endpoint, at weeks 1, 2 and 8).

Statistical Analysis Plan (SAP)

7. The proportion of subjects with ≥ 2 point reduction in FWS score (at maximum frown) in the BoNT/A-DP and placebo groups during the first treatment cycle visit relative to baseline, based on the independent rater's assessment of photographs (at baseline and visits 2, 4, 12, 16 and 20 weeks after treatment, within the first treatment cycle).
8. Time to onset of effect in the BoNT/A-DP and placebo groups in the first treatment cycle, as measured at weeks 1, 2 and 4 based separately on subject and investigator assessments. Onset of effect defined as at least a 1 point improvement in FWS score from baseline (at maximum frown). In addition, onset of effect will be assessed by subjects daily in the first 2 weeks after treatment, by recordings in the subject diary.
9. The extent of subject perceptions of effect of, and satisfaction with, treatment, in the BoNT/A-DP and placebo groups, during each treatment cycle, as assessed by the FACE-Q Satisfaction with Outcome Scale.
10. The proportion of subjects with a ≥ 1 point reduction in FWS score at rest in the BoNT/A-DP and placebo groups, relative to baseline, during the first treatment cycle, based on the independent rater's assessment of photos.
11. The percentage of subjects with a FWS score of 0 or 1 and an improvement of ≥ 2 points in FWS score at maximum frown (investigator and subject assessment) at four weeks after re-treatment relative to the rating at the preceding end of cycle visit.

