8.6.1.1 Multiplicity

The testing of the primary and the five key secondary efficacy endpoints will be performed with appropriate multiplicity control based on the FAS population. The results of each test result will only be considered confirmative if the previous test in the order showed a confirmatory result at a one-sided significance level of 0.025. If the one-sided p-value is larger than 0.025 for any of the tests, the results of the subsequent tests will only be considered exploratory, and not confirmatory. The application of this hierarchical approach keeps the global significance level to 0.025 one-sided and requires no further adjustment of the significance level.

The following order of tests will be applied:

- Primary endpoint (composite endpoint)
- Key secondary endpoint 1 (composite endpoint)
- Key secondary endpoint 2 (composite endpoint)

Statistical Analysis Plan (SAP)

- Key secondary endpoint 3
 - 3.1: The investigator's in-clinic assessments
 - 3.2: The subject's in-clinic assessments
- Key secondary endpoint 4 (composite endpoint)
- Key secondary endpoint 5
 - 5.1: The modified Skindex-16 (GL-QoL) Emotional domain
 - 5.2: The modified Skindex-16 (GL-QoL) Functioning domain
 - 5.3: The modified Skindex-16 (GL-QoL) Overall score
 - 5.4: The FACE-Q Appraisal of Lines Between Eyebrows scale
 - 5.5: The FACE-Q Age Appraisal VAS score

All other analyses (e.g., additional analyses of the primary and the five key secondary efficacy endpoints using other analysis populations or other statistical methods, analyses of additional secondary endpoints) will only be considered exploratory.

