8.6.4 Additional secondary analyses

The additional secondary efficacy endpoints will be analyzed applying the appropriate statistical method for the comparison of both treatment arms. For proportions

- of responders with a FWS score of 0 or 1 and an improvement ≥ 2 points in FWS score at maximum frown,
- of subjects with ≥ 2 point reduction in FWS at maximum frown,
- of subjects with a ≥ 1 point reduction in FWS at rest, and
- of subjects with an improvement of ≥ 2 points in FWS at maximum frown at 4 weeks after re-treatment,

the Cochran-Mantel-Haenszel test (with stratification variable site) and the Pearson χ^2 -test will be applied. In case of a total number of observations below 30, or in case of at least one cell frequency below 5, Fisher's exact test will be used instead of the χ^2 -test. Two-sided 95% CIs for response rates will be calculated, where appropriate. Additionally the cumulative proportions of effects at weeks 1, 2, and 4 will be calculated. Time to onset of effect in the first treatment cycle will be analyzed descriptively and by using the Kaplan-Meier method. Moreover, the daily assessments of the line severity when frowning will be analyzed descriptively. The FACE-Q satisfaction with outcome scale will be analyzed descriptively.

All endpoints, with exception of “responder” 4 weeks after re-treatment, will be analyzed for the first treatment cycle only. The analysis of “responder” 4 weeks after re-treatment will be conducted on observed values only, i.e. subjects with missing investigator or the subject in-clinic assessments on FWS week 4 or at the preceding end of the cycle visit will be excluded from analysis. Subjects who were treated with placebo during the first treatment cycle are excluded from the analysis of this endpoint, but not assigned as being non-responders. A two-sided McNemar test (using a significance level of 0.05) will be used to compare the response proportions between week 4 re-treatment visit and at the preceding end of the cycle visit. This endpoint will be separately analyzed for each open label extension cycle.

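### Endpoint 7 compares the arms on photo ratings at weeks 12, 16 and 20, but only one late photo per subject is read, and the timing of that subject's relapse decides which one

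*Protocol*

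**What the plan says.** **Endpoint.** Endpoint 7 (Protocol synopsis and 6.4.2.2; SAP 4.3) is the proportion in each arm with a reduction of at least 2 points in FWS score at maximum frown, rated independently from photographs. The time points are given as "at baseline and visits 2, 4, 12, 16 and 20 weeks after treatment, within the first treatment cycle". Endpoint 10, the at-rest counterpart, names no weeks; it is assessed "relative to baseline, during the first treatment cycle, based on the independent" rater.

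**Test.** For these proportions SAP 8.6.4 applies "the Cochran-Mantel-Haenszel test (with stratification variable site) and the Pearson" chi-square test, switching from chi-square to Fisher's exact test when numbers are small.

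**Which photos are read.** Protocol 10.1.2 has photographs taken at baseline, weeks 2 and 4, and every cycle 1 evaluation for re-treatment. Baseline, week 2 and week 4 photos are read for everyone. Beyond those, "only the photograph of the visit preceding the re-treatment visit will be reviewed by the independent raters". The same limit stands in footnote 10 of Protocol 2.1, footnote 12 of Protocol Table 9-1, and footnote 10 of SAP Table 1 ("only the photo of the visit preceding the re-treatment visit will be reviewed by the independent reviewers").

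**What triggers re-treatment.** Under Protocol 7.3 the lines "must have relapsed to a FWS score of 2 or 3 as determined by both the investigator and the subject".

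**Status.** SAP 8.6.1.1 says that "analyses of additional secondary endpoints) will only be considered exploratory".

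**The concern.** The endpoint needs a rating from every subject, or at least from an unselected set, at weeks 12, 16 and 20. The reading rule gives at most one late photo visit per subject, and the re-treatment date picks it. That date depends on relapse in line severity, which is what the endpoint measures.

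A late photo response rate would therefore describe subjects who, in general, did not qualify for re-treatment at that visit and did at the next. Early relapsers and the longest responders are both left out. A p-value from this set would look like a randomized comparison without being one. Fisher's test deals with sparse cells, not with selection. These are also the only efficacy ratings made by independent raters.

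**Working it through.** **1. Which late photo is read.** This step needs no assumed rates. Inputs: evaluation visits at week 12 and every 4 weeks after that (Protocol 6.3.2), and no photography at the week 8 visit (Protocol Table 9-1, Visit 6).

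| Re-treated at | Late photo read |
|---|---|
| Week 12 | None (preceding visit is week 8) |
| Week 16 | Week 12 only |
| Week 20 | Week 16 only |
| Week 24 | Week 20 only |
| After week 24 | None of weeks 12, 16, 20 |
| Never | Not defined |

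The three late samples are disjoint, and each is defined by an event after randomization.

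**2. Whether another rule repairs this.** The missing-data rules (Protocol 12.3; SAP 7.2.1) cover in-clinic FWS ratings. For the in-clinic responder analyses at weeks 16 and 20, subjects re-treated earlier count as non-responders (Protocol 12.4.2; SAP 8.6.3). At other cycle 1 visits SAP 8.6.3 excludes them. Neither convention is assigned to photographs, and SAP Section 9 lists no change on this point.

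**3. How many active photos would be read.** The plan gives no figure, so these are illustrations. Let T be time to relapse, normal with SD 6.5 weeks. The share read at week w is P(w < T ≤ w+4). Protocol 4.5.1.2 cites durations of 17.1 ± 6.5 weeks and, from another source, a median of 12.1 weeks.

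- Mean 17.1: 21.6% re-treated at week 12. Read at weeks 12/16/20: 21.6/23.9/18.4%, which × 525 gives about 114/126/96.
- Mean 12.1, same SD: 49.4% re-treated at week 12. Read: 23.2/16.2/7.9%, about 122/85/41.
- Multiplying by 0.9 × 0.6 = 0.54 (the plan's 10% dropout and 60% response, with every non-responder assumed re-treated at week 12) gives 11.7/12.9/9.9% or 12.5/8.8/4.2%.

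**4. How many placebo photos would be read.** Let f be the share not qualifying at week 12 (assumed 0.05-0.30) and q the share of those remaining who qualify at each next visit (assumed 0.3-0.7).

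- Week 12: 175fq = 2.6 to 36.8
- Week 16: 175f(1−q)q = 1.8 to 13.1
- Week 20: 175f(1−q)²q = 0.6 to 7.8

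Over about 18 sites the upper ends average 36.8/18 = 2.0, 13.1/18 = 0.7 and 7.8/18 = 0.4 placebo photos per site, for a site-stratified test.

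**5. What selection can do to the contrast at week 12.** Let r be the true responder share, i the share of non-responders not yet eligible, and h_r and h_i the shares of those two groups re-treated at week 16. The rate among photos read is r·h_r / (r·h_r + i·h_i).

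- Take r = 0.30 active and 0.02 placebo, i = 0.20 and 0.03, h_r = h_i = 0.5. Active: 0.15/0.25 = 60%, with 0.25 × 525 = 131 read. Placebo: 0.010/0.025 = 40%, with 0.025 × 175 = 4.4 read. A true difference of 28 points becomes 20, resting on about 4 placebo subjects.
- With r = 0.30 and 0.03, i = 0.20 and 0.02, both read rates are 60%. A true difference of 27 points becomes 0.
- Over all the scenarios tried (r 0.20-0.40 active, 0.02-0.03 placebo), 4-11 placebo subjects are read. The difference among photos read runs from 0 to 37 points, against 18 to 37 in all randomized subjects.
- Counting unread photos as non-response does not help. In the first scenario's rates, 30% against 2% becomes r·h_r = 9-15% against 0.6-1.0% for h_r of 0.3-0.5, because subjects whose effect outlasts week 16 are scored as failures at week 12.

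**The case against.** **It is exploratory.** True. No confirmatory claim uses photographs, and the duration objective rests on investigator and subject ratings. That limits the weight of the point, but the between-arm tests are still planned and would be reported.

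**The selective reading is deliberate.** Footnote 10 of Protocol 2.1 says the photo is there to confirm that the subject did not yet qualify. That purpose is sound, but it does not supply the data endpoint 7 calls for.

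**The preceding visit could mean the same-day evaluation,** since evaluation, end of cycle and re-treatment fall on one day. The footnote's stated purpose points to the earlier visit. On the same-day reading the counts would change, but the photo would be taken at relapse, so selection on outcome would remain.

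**The numbers are soft.** This largely stands. Treating 12.1 weeks, reported as a median, as a normal mean with another source's SD is crude. The 0.54 factor equates non-response with eligibility: a subject going from FWS 2 to 1 is a non-responder but cannot be re-treated. It also applies whole-study dropout by week 12. The placebo inputs have no source in the documents, and the per-site figures are averages, not caps. None of these numbers is needed for the conclusion, which follows from steps 1 and 2.

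**Endpoint 10 contradicts nothing.** Correct, because it names no weeks. Any late photo data used for it would share the defect.

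**Conclusion.** The concern holds. The late time points of endpoint 7 cannot be analysed as a randomized comparison under the reading rule, and the protocol and SAP both carry the two incompatible provisions. This follows from the documents' own visit, photo and re-treatment rules.

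The size depends on assumptions. Roughly a quarter or fewer of active subjects would contribute at any one late visit under the two relapse distributions (up to 34% at week 12 in the step 5 scenarios). Placebo would contribute from a handful to a few tens of subjects at week 12 and fewer later. The primary endpoint, the hierarchical tests and the week 2 and 4 photo results are unaffected. It should be corrected, but it does not threaten the trial's main conclusion.

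**What to change.** **Main change.** Remove weeks 12, 16 and 20 from endpoint 7 (Protocol synopsis and 6.4.2.2; SAP 4.3), name weeks 2 and 4 for endpoint 10, and limit the between-arm photo tests in SAP 8.6.4 to those two visits. Report the single pre-re-treatment photo descriptively, which keeps its stated purpose. The cost is wording only, with the changed time points recorded as a change to the planned analysis. It gives up late photo comparisons that are not valid as written.

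**Alternative, if late photo comparisons are wanted.** Have the existing raters read all cycle 1 photos already taken at weeks 12, 16 and 20, and state that subjects re-treated before a visit count as non-responders there, as the plan already does for in-clinic weeks 16 and 20. At week 12 that convention is not needed, because no re-treatment comes earlier. From week 16 it means many outcomes are set by in-clinic ratings and not by the blinded photo rater: if 70-95% of placebo subjects are re-treated at week 12, that is 175 × 0.70 to 175 × 0.95, about 123-166 subjects. The cost is extra reading time.

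Neither option needs a new visit or photograph. Either should be settled before unblinding.
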